#### 2.1.1. Subgroups of interest

Subgroup analyses will be performed for selected efficacy variables. The FAS can be stratified into two CFI variant subgroups: **CFI rare variant** subgroup of patients with rare variant resulting in CFI haploinsufficiency, and **Broad GA** subgroup including the rest of patients in the study;

### 2.2. Protocol deviations

Protocol deviations will be identified and recorded by the study monitor in the Monitoring Visit Reports and/or the electronic data capture (EDC) system. Prior to locking the database for the analyses supporting clinical study reports, the relevant important protocol deviations will be identified. They will be classified as CSR non-reportable or CSR reportable based on their effect on the rights, safety, or wellbeing of the subjects and/or the quality and integrity of the data. CSR reportable protocol deviations will be summarized for SAF. The CSR reportable protocol deviations based on SAF will be provided in a listing.

No exclusions of patients from SAF and FAS will occur due to protocol deviations.

Alternative treatment for GA in the study eye during long-term follow up is not prohibited in the protocol but cannot be excluded. In this case efficacy and assay variables will be censored at last observation prior to the start of the alternative treatment. The censoring of data in such cases will be derived from concomitant medication data.

## Statistical Analysis Plan

Sponsor:	Gyroscope Therapeutics		
Protocol:	GT005-01 (FOCUS)		
Document Version No.:	04.0	Document Date:	17-JUN-2024

### 3. STATISTICAL METHODS

#### 3.1. General information

Two interim analyses and a clinical study report (CSR) are planned. First interim analysis will include data up to Week 72 from cohorts 1-4 with GT005 delivered via the transvitreal procedure. Second interim analysis will include data from cohorts 1-4 up to Week 96 and from Orbit SDS administration cohorts 5-7 up to Week 48. Clinical study report will be based on the analysis of all variables specified in this SAP from all 7 cohorts on data over 96 weeks.

All outputs will be incorporated into Word files and PDF files, sorted and labeled according to the International Conference on Harmonisation (ICH) recommendations, and formatted to the appropriate page size(s).

Tabulations will be produced for appropriate demographic, baseline, efficacy, biomarker assay, and safety parameters. For categorical variables, summary tabulations of the number and percentage within each category (with a category for missing data) of the parameter will be presented. For continuous variables, the number of observations, mean, median, quartiles, standard deviation, standard error (SE), minimum and maximum values will be presented. Where appropriate, 95% confidence intervals (CIs) for point estimates of the mean or proportion will be provided. Data will be listed and summarized using descriptive statistics by dose, by route of administration, and by assessment visits as appropriate. Efficacy and biomarker assay data will additionally be summarized by CFI rare variant and broad GA subgroups. All ocular evaluations and ocular adverse events, where appropriate, will be presented by eye (Study Eye, Fellow Eye).

No formal statistical hypothesis testing will be performed for this study.

Medical history, concurrent procedures and adverse events will be coded using the Medical Dictionary for Regulatory Activities (MedDRA). Prior and concomitant medications will be coded using World Health Organization (WHO) Drug Reference List dictionary version Mar 2020.

All statistical analyses will be performed using SAS statistical software (Version 9.4), unless otherwise noted.

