11.3. Statistical Analysis

The detailed statistical analyses will be outlined in the SAP.

The main analysis will be performed at the conclusion of the study (Week 240), after which a clinical study report (CSR) will be prepared. Interim analyses may be considered to help inform internal development decision points for GT005, in which case the details will be pre-specified in the SAP prior to conducting the analysis. Additionally, a safety focused analysis will be conducted to enable the independent data review by a DSMB after three subjects in Cohorts 1 to 3 and Cohort 5 have completed the 5-week post-surgery visit. Additional DSMB meetings may be held as needed or as requested by the DSMB members. Full details can be found in the DSMB Charter.

Analyses of data involving the Orbit SDS is US-specific.

For the main statistical analysis and CSR, all efficacy (anatomical and functional visual outcomes) and safety data will be listed and summarised using descriptive statistics by dose and route of administration, and by assessment (Visits 1 to 8). The Long-term follow-up data (Visits 9 to 13) will be reported separately using descriptive statistics by dose and route of administration and by assessment. Additionally, for all ocular evaluations and tests, and ocular AEs, where appropriate these will be additionally presented by eye (Treated [Study Eye]/Untreated [Fellow Eye]). The descriptive summary for the categorical variables will include subject counts (n) and percentages and, if appropriate, frequency of events. The descriptive summary for the continuous variables will include counts (n), means, medians, standard deviations and minimum and maximum values. Where possible, all data from subjects who withdraw prematurely from the study will be included in any presentations. Further details on the handling of withdrawals and/or missing data will be specified in the SAP.

Subgroup analyses will be performed, if appropriate, to evaluate some of the efficacy endpoints across subgroups defined by genetic classification: e.g., a rare variant resulting in CFI haploinsufficiency and those without.

Graphical displays appropriate to the types of data may be used to present any important findings.

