Any deviations from the planned analyses detailed in the protocol will be documented in the SAP and final CSR. If the study is prematurely discontinued, all available data will be listed and a review will be carried out to determine which statistical analyses are considered appropriate.

11.3.1. Demographics and Baseline Characteristics:

Surgical details and measures at baseline including: demographics, medical/surgical history, concomitant medication, laboratory safety, and urine pregnancy testing will be summarised descriptively by dose and route of administration. No formal comparisons between Cohorts will be made. Assessments made at screening/baseline and also post-surgery will only be included in their respective safety and efficacy tables, together with post-baseline assessment values.

A medication given prior to the injection of study drug during surgery will be classified as a prior medication. A medication given with or after the injection of study drug will be classified as concomitant. Prior medications continuing during the study will be labelled accordingly in the listings.

Verbatim medical/surgical history terms will be coded (to preferred terms) using terminology from MedDRA. Medications will be coded using the World Health Organisation Drug Dictionary to Anatomical Therapeutic Chemical classification level 2 (therapeutic main group) and preferred term.

Additionally, the last visual acuity values measured using the BCVA ETDRS prior to surgery will be presented with the baseline data by dose and route of administration and by eye (Treated [Study Eye]/Untreated [Fellow Eye]). Genetic testing will also occur prior to surgery but to ensure subject confidentiality, the distribution of these data will be carefully controlled. Further details of the procedures required for maintaining the subject's genetic profile confidentiality will be discussed in greater detail in the SAP.

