### 1. INTRODUCTION

This Statistical Analysis Plan (SAP) describes the statistical methodology and data handling of the data collected in the clinical trial for Gyroscope Therapeutics with Protocol GT005-01: FOCUS: An open label first in human Phase I/II multicentre study to evaluate the safety, dose response and efficacy of GT005 administered as a single subretinal injection in subjects with Macular Atrophy due to Age-related Macular Degeneration (AMD). This SAP is based on the Clinical Study Protocol v 9.0, dated 15 December 2022.

The planned analyses identified in this SAP provide the basis for the results section of the clinical study reports and may be used in regulatory submissions or publications. Any differences in the planned analyses relative to the study protocol will be highlighted in the CSRs.

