### 4. CHANGES TO PLANNED ANALYSES

As of this date, there have been no changes between the protocol-defined statistical analyses and those presented in this statistical plan.

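### SAP Section 4 reports no change from the protocol, but the only CSR the SAP describes covers 96 weeks and no summary is assigned to Weeks 144, 192 and 240

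*SAP*

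**What the plan says.** **Protocol 11.3** fixes the timing: "The main analysis will be performed at the conclusion of the study (Week 240), after which a clinical study report (CSR) will be prepared". For content, the main analysis and CSR summarise data by assessment for Visits 1 to 8, that is, to Week 48. For the remaining visits, "The Long-term follow-up data (Visits 9 to 13) will be reported separately", using descriptive statistics by dose and route. The section ends with two rules. The first is "Any deviations from the planned analyses detailed in the protocol will be documented in the SAP and final CSR". The second covers early stopping: "If the study is prematurely discontinued, all available data will be listed and a review will be carried out", to decide which analyses are appropriate.

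**SAP 3.1** says: "Two interim analyses and a clinical study report (CSR) are planned". The first interim runs to Week 72 for Cohorts 1 to 4. The second runs to Week 96 for Cohorts 1 to 4 and to Week 48 for Cohorts 5 to 7. Then: "Clinical study report will be based on the analysis of all variables specified in this SAP from all 7 cohorts on data over 96 weeks".

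**SAP Table 1** keeps the protocol's 240-week horizon for four secondary criteria: TEAEs and TESAEs, BCVA and LLVA, microperimetry, and GA area.

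**SAP Section 4**, headed as the place for changes to planned analyses, says that "there have been no changes between the protocol-defined statistical analyses and those presented in this statistical plan". The SAP Introduction adds: "Any differences in the planned analyses relative to the study protocol will be highlighted in the CSRs".

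**The concern.** Section 4 is where a reader looks for departures from the protocol. Anyone relying on it would not learn that the CSR is now built on a 96-week window. Nor would they learn that the protocol's separate long-term summary has no counterpart in the SAP for its last three visits.

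Long-term safety up to 240 weeks is a named secondary objective, and GT005 cannot be removed once injected (Protocol 4.4). If the horizon was shortened on purpose, the SAP should say so and give the reason. If it was not, an analysis is missing. At stake are traceability and the match between the endpoints as defined and the tables that will be produced.

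**Working it through.** The SAP states no figure to reproduce, so the check sets the two documents side by side and counts.

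**1. Main analysis, CSR and visits**

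| Item | Protocol 11.3 | Visible SAP |
|---|---|---|
| Timing or window of the CSR | Prepared after the main analysis at Week 240 | Data over 96 weeks, all seven cohorts |
| Visits 1 to 8 (to Week 48) | Summarised in the main analysis | Inside the CSR window |
| Visits 9 and 10 (Weeks 72, 96) | Summarised separately | Inside the CSR window; separate reporting not mentioned |
| Visits 11 to 13 (Weeks 144, 192, 240) | Summarised separately | No summary assigned |

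- Latest cutoffs of the three SAP analyses: Week 72, Week 96 and Week 96. None is later than Week 96 (0 of 3).
- Long-term visits (Protocol 3.1): Weeks 72, 96, 144, 192 and 240, so five. Two fall at or before Week 96; 5 − 2 = 3 fall after it.
- Calendar: 240 − 96 = 144 weeks, and 144/240 = 60% of the planned follow-up period. This does not measure lost data, because follow-up past Week 48 needs further consent.

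**2. Criteria in SAP Table 1**

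- With a 240-week horizon: TEAE/TESAE, BCVA/LLVA, microperimetry and GA area, so 4.
- With no stated window: BSS delivery, GT005 delivery and device-related events, so 3.
- Visible total: 4 + 3 = 7. Redacted endpoints could add to either group.

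SAP 3.2 and 3.9.1 put all CRF data and all adverse events into listings. Later data held in the database could therefore be listed, but a listing is not the descriptive summary that the protocol plans.

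**3. Other differences that Section 4 omits**

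| Item | Protocol | SAP |
|---|---|---|
| Medical history | Summarised by dose and route (11.3.1) | Listed only (3.6) |
| Concomitant medication | Summarised by dose and route (11.3.1) | Listed only (3.11) |
| Haematology and chemistry | Descriptive statistics and change over time (11.3.4.3) | Boxplots of change for the Table 6 tests and counts of notable values; no by-visit tables (3.9.3) |

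These do not depend on the data cut, so the Section 4 statement would be wrong even if the 96-week window had always been intended.

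**4. Duty to document**

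Protocol 11.3 asks for deviations to be recorded in two places, the SAP and the final CSR. The SAP Introduction undertakes the second. Section 4 is where the first would be met, and it denies that there is anything to record. The SAP cites Protocol v9.0, so an older protocol version does not explain the mismatch.

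**The case against.** Several points on the other side have force.

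- **CSR timing is not CSR content.** A reader might infer that the CSR's summaries shrank from 240 weeks to 96. The protocol does not support that: its main summaries cover Visits 1 to 8 only, so the SAP's CSR window is wider than those. What changed is when the CSR falls and how Visits 9 to 13 are handled.
- **Another report may exist.** The SAP speaks of clinical study reports in the plural, and its by-visit methods carry no Week 96 cap. A reader should therefore not conclude that Weeks 144 to 240 will never be summarised. But the SAP describes one CSR and names no later report or later plan.
- **The limits are soft.** A horizon worded as an upper limit, with further consent needed after Week 48, promises less than complete 240-week data. It does not say that summaries stop at Week 96.
- **Early discontinuation.** If the protocol's clause applied, a reduced analysis would follow the protocol's own rule. The visible text does not say whether it did. Gaps in the visible SAP history cannot be held against the plan.
- **Primary endpoint.** A reader might infer that the 48-week incidence will be tabulated to Week 96. The documents do not establish this. SAP 3.9.1 summarises TEAEs at analysis timepoints that it does not define and that could include Week 48, and SAP 3.10 already uses two safety cutoffs within one interim. The term needs defining; no distortion is shown, and with no event rates given none can be sized.

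The promise to highlight differences in the CSRs limits the harm but does not make Section 4 correct.

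**Conclusion.** The contradiction stands and should be fixed. As written, the visible SAP produces no summary for three of the five long-term visits, keeps four of seven visible secondary criteria at 240 weeks, and states that nothing differs from the protocol. Three further reductions, in medical history, concomitant medication and by-visit laboratory summaries, also go unrecorded.

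The conclusion is limited to what this SAP says. It assumes that no removed or redacted text assigns Weeks 144 to 240 to another report or invokes the discontinuation clause. Confidence in the mismatch between Protocol 11.3, SAP 3.1 and SAP Section 4 is high. The primary-endpoint window is a minor clarification only.

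SAP 3.1 rules out formal hypothesis testing and no sample size was calculated, so no alpha or power is affected.

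**What to change.** 1. Replace the Section 4 statement with the actual differences from the protocol: the timing and data window of the CSR, the handling of Visits 9 to 13, and the summaries of medical history, concomitant medication and laboratory values that became listings or plots.
2. Either specify descriptive summaries of Weeks 144, 192 and 240, in this plan or in a named later report, or restate the four criteria in Table 1 as summarised to Week 96 with the reason, citing the discontinuation clause of Protocol 11.3 if it applied.
3. As a minor clarification, define the analysis timepoints in SAP 3.9.1. State that the CSR's primary-endpoint tables count TEAEs and TESAEs through Week 48, with later events shown separately.

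**Cost.** Items 1 and 3 are SAP wording plus a few table cuts. SAP Table 5 marks 3+3+2+2+2+3+2+2+2 = 21 tables. The primary endpoint needs 6 of them at Week 48: all AEs and SAEs by system organ class and preferred term (2 types), each for study eye, fellow eye and non-ocular events (2 × 3 = 6). For item 2, summaries to Week 240 need data that may not all be available; if they are dropped, the cost is an open statement that the long-term window was shortened.

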##### 3.1.1. Study days and visit windows

Study day is defined as the number of days relative to the date of the subretinal injection with the study drug. For a particular date, study day will be calculated as follows:

- for dates on or after the date of study treatment: Study day = Assessment date – Date of treatment administration + 1;
- for dates prior to the date of administration of study treatment: Study day = Assessment date – Date of treatment administration.

Baseline values are defined as values from the last assessment prior to surgery for the study treatment administration. All data collected after the treatment administration are defined as post-baseline.

The end of study date is the date when a patient completes or discontinues the study. For reporting data by visit in outputs, the end of study visit will be allocated to the actual (reported) visit number. If the end of study date is not on a scheduled visit, then the end of study visit will be allocated, based on study day, to the closest future scheduled study visit.

For scheduled visits, the analysis visits will be the actual (reported) visits.

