
[REDACTED]
	

[REDACTED]
	

[REDACTED]
	

Table 3: Follow-up Schedule (Week 72 to Week 240)

Assessment	Local Trial Site ¹					Unscheduled Visit/ Early Termination ²
	Visit 9 Week 72 (Year 1.5) ±30 days	Visit 10 Week 96 (Year 2) ±30 days	Visit 11 Week 144 (Year 3) ±30 days	Visit 12 Week 192 (Year 4) ±30 days	Visit 13 Week 240 (Year 5) ±30 days	
Standard ophthalmic examination	X	X	X	X	X	X
Colour fundus photography	X	X	X	X	X	X
Fundus autofluorescence	X	X	X	X	X	X
OCT macula	X	X	X	X	X	X
OCT-A ³			X ⁴			X ⁴
Fluorescein angiography ³			X ⁴			X ⁴
Visual acuity: BCVA/LLVA using ETDRS	X	X	X	X	X	X
Microperimetry	X	X	X	X	X	X
Additional functional assessments (if required) ⁶	X	X	X	X	X	X
AE/SAE monitoring ⁷	X	X	X	X	X	X
Concomitant medication	X	X	X	X	X	X
Submission of historical FAFs and/or OCTs ⁹				X		
Abbreviations: AAV2=adeno-associated virus vector serotype 2; AE=adverse event; BCVA=best corrected visual acuity; CFI=complement factor I; CNV=choroidal neovascularisation; ETDRS=early treatment diabetic retinopathy study chart; FA=fluorescein angiography; LLVA=low luminance visual acuity; MNRead=Minnesota low vision reading; OCT=optical coherence tomography; OCT-A=optical coherence tomography angiography; SAE=serious adverse event; [REDACTED] [REDACTED].						
1. Dependent upon location and Sponsor approvals, a Surgical Site may also act as a Local Site						
2. Minimum study assessments shown; additional assessments may be performed if clinically indicated. [REDACTED]						
3. Other imaging modalities may be performed to assess for CNV if OCT-A is not available. In the event that the OCT/OCT-A images are inconclusive to rule out the presence of CNV the subject will be required to undergo an additional assessment via FA. At the Investigator's discretion, FA may also be performed initially prior to the OCT/OCT-A results being available, but this is not mandatory.						
4. OCT-A and/or fluorescein angiography may be performed during the study period if clinically indicated, for example, if a subject converts to wet AMD.						

Assessment	Local Trial Site ¹					Unscheduled Visit/ Early Termination ²
	Visit 9 Week 72 (Year 1.5) ±30 days	Visit 10 Week 96 (Year 2) ±30 days	Visit 11 Week 144 (Year 3) ±30 days	Visit 12 Week 192 (Year 4) ±30 days	Visit 13 Week 240 (Year 5) ±30 days	
7.	Additional tests/assessments (i.e., blood tests, imaging or functional assessments) may be conducted, as needed, to allow for safety monitoring.					

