[REDACTED] The surgery will be performed under local anaesthesia. Other anaesthetic options will be considered by the surgeon as appropriate for the subject. Then subjects will receive GT005 at one of the three doses ([REDACTED]) as a single administration in the form of a subretinal injection of 100 microlitres.

After surgery, subjects will remain in the clinic for up to 24 hours following the surgery to assess any acute issues resulting from the surgery. [REDACTED]

[REDACTED]

Subjects will undergo follow-up visits at Week 1, 5 and 8 post-dosing, every three months (at Weeks 12, 24, 36, and 48) for the first year, and at Weeks 72 (1.5 years), 96 (2 years), 144 (3 years), 192 (4 years), and 240 (5 years) post-dosing. At the Week 48 visit, subjects will be invited to consent to the additional follow-up (up to and including Week 240 visit). The Week 48 visit will be the time point used for the primary endpoint of the study. Week 240 (Year 5) will be the end of study visit.

Assessments carried out at the follow-up visits include ophthalmic examination, measurements of the size of GA, retinal examination, microperimetry, visual acuity (BCVA and LLVA) and [REDACTED] Blood samples will be taken for safety [REDACTED]

[REDACTED]

(as described in the Schedule of Assessments).

[REDACTED]

If a subject drops out or is withdrawn from the study, prior to the Week 48 visit, every reasonable effort will be made to complete the assessments scheduled for the Early Termination Visit.

If a subject does not agree to consent to long-term follow-up as part of this study, any ongoing AEs will be followed until resolution with subject consent.

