7.18. Early Termination Visit

Subjects have the right to withdraw from the study at any time and for any reason. If a subject refuses to be seen for further visits, the assessments listed in the early

termination visit should be performed at the time they have indicated that they will not attend for further visits.

Where a subject is withdrawn from the study at their own request or based on a decision of the Investigator, follow-up may be maintained, which may include telephone calls or follow-up visits arranged by the investigator, subject to the consent of the participant.

7.18.1. Prior to Week 48 Visit:

In the event that a subject discontinues the study prior to Week 48 visit, the site should use every reasonable effort to ensure that an Early Termination Visit is conducted. The following assessments should be performed:

Recording of: concomitant medication, vital signs, AEs.

The following procedures will be carried out:

- Blood draw for:
 - Biochemistry and haematology
 - [REDACTED]
 - [REDACTED]
 - [REDACTED]
- Standard ophthalmic examination
- CFP
- FAF
- OCT macula
- [REDACTED]
- OCT-A if clinically indicated (if a subject converts to wet AMD)
- FA if clinically indicated (if a subject converts to wet AMD). FA is only required if OCT/OCT-A images are inconclusive to rule out the presence of CNV. However, FA may also be performed prior to the OCT/OCT-A results being available, but this is not mandatory
- Microperimetry. **Note: microperimetry is only applicable at sites with a MAIA microperimeter**
- Visual acuity (BCVA and LLVA) using ETDRS
- [REDACTED]
[REDACTED]
[REDACTED]
- [REDACTED]

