7.18.2. Post Week 48 to Week 240 Visit

In the event that a subject discontinues the study after Week 48 and before Week 240 visit, the site should use every reasonable effort to ensure that an Early Termination Visit is conducted. The following assessments should be performed:

Recording of: concomitant medication, vital signs, AEs.

The following procedures will be carried out:

- Blood draw for:
 - Biochemistry and haematology
 - [REDACTED]
 - [REDACTED]
 - [REDACTED]
- Standard ophthalmic examination
- CFP
- FAF
- OCT macula
- [REDACTED]
- OCT-A if clinically indicated (if a subject converts to wet AMD)
- FA if clinically indicated (if a subject converts to wet AMD). FA is only required if OCT/OCT-A images are inconclusive to rule out the presence of CNV. However, FA may also be performed prior to the OCT/OCT-A results being available, but this is not mandatory
- Microperimetry. **Note: microperimetry is only applicable at sites with a MAIA microperimeter**
- Visual acuity (BCVA and LLVA) using ETDRS
- [REDACTED]

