## Statistical Analysis Plan

Sponsor:	Gyroscope Therapeutics		
Protocol:	GT005-01 (FOCUS)		
Document Version No.:	04.0	Document Date:	17-JUN-2024

Data collected at unscheduled visits will not be used in 'by-visit' tabulations or graphs but will be included in analyses based on all post-baseline values such averages over a given period or summaries of maximum/minimum values. These unscheduled visits data will not be used in analyses with mixed model for repeated measures (MMRM). All data collected at unscheduled visits will be included in the listings.

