### 3.7. Efficacy analyses

Efficacy analyses will be conducted using the FAS by treatment dose and route of administration.

**GA area (mm^2)** change from baseline in the study eye as assessed by FAF will be presented in spaghetti plots and in a summary by visit table. It will also be summarized in a table and line plots as least-squares means with 95% CI by visit using MMRM model with fixed effects for treatment (defined as dose and route of administration), study visit, baseline GA area (mm^2), treatment by visit interaction and visit by baseline GA area interaction.

**Square root of GA area (mm)** change from baseline in the study eye will be presented in spaghetti plots and in a summary by visit table. It will also be summarized in a table and line plots as least-squares means with 95% CI by visit using MMRM model with fixed effects for treatment, study visit, square root of baseline GA area (mm), treatment by visit interaction and visit by square root of baseline GA area (mm) interaction. MMRM analysis will be repeated for CFI rare variant subgroups and [REDACTED] by replacing in the model treatment with subgroups of interest.

For MMRM analysis an unstructured covariance matrix will be used to model the within-patient error. If an MMRM model with an unstructured covariance matrix does not converge, a more restricted covariance matrix can be considered in the following order until convergence is reached: first-order autoregressive, Toeplitz, compound symmetry and variance components.

Additionally, scatter plots with linear trend lines for square root of GA area size (mm) change from baseline at the target analysis visit vs. last observed CFI levels before the target analysis visit in the vitreous and aqueous samples will be generated by treatment groups.

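### Off-schedule end-of-study images move to the next scheduled visit with no window limit; if this rule rather than the unscheduled-visit exclusion governs, absolute GA growth is understated

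*SAP*

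**What the plan says.** SAP 3.1.1 keeps an end-of-study visit at its reported visit number when it coincides with a scheduled visit. When it does not, "the end of study visit will be allocated, based on study day, to the closest future scheduled study visit". The move is always forward. Although the section heading mentions visit windows, no window or maximum distance is given.

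The closing paragraph of SAP 3.1.1 keeps unscheduled-visit data out of by-visit tables and graphs, and adds: "These unscheduled visits data will not be used in analyses with mixed model for repeated measures (MMRM". It does not say whether an early-termination visit counts as unscheduled.

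The protocol gives unscheduled visits (7.17) and early termination (7.18) separate sections, and Tables 1 and 2 give early termination its own column. Table 3, which covers the period after Week 48, merges them under "Unscheduled Visit/ Early Termination".

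Protocol 7.18.1 and 7.18.2 both put FAF on the early-termination list. The second covers a subject who "discontinues the study after Week 48 and before Week 240 visit". Long-term visits fall "at Weeks 72 (1.5 years), 96 (2 years), 144 (3 years), 192 (4 years), and 240 (5 years) post-dosing". The tolerance is 7 days at Weeks 12 to 48 and 30 days from Week 72 ("Visit 9 Week 72 (Year 1.5) ±30 days").

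SAP 3.7 analyses GA change with "fixed effects for treatment (defined as dose and route of administration), study visit, baseline GA area" and two interactions with visit. It has no term for actual time.

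**The concern.** GA lesions grow, so an image taken at Week 50 and filed under Week 72 shows less change than Week 72 would. The model knows only the visit label and treats the value as an observed Week 72 value. Because the move is always forward, the error always leans towards less growth and does not average out across subjects.

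Two programmers reading SAP 3.1.1 could also handle the same image differently. One would relabel it and use it; the other would drop it from by-visit outputs and the MMRM.

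The rule also ignores which tests a visit contains:

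- Early termination between Weeks 5 and 8 sends FAF to Week 8, which has none (Protocol 7.7, Table 2).
- Early termination between Weeks 24 and 36 sends microperimetry to Week 36, which has none (Protocol 7.10, Table 2).
- Early termination in the first 8 weeks sends LLVA to Week 1, 5 or 8, where Table 2 footnote 12 says it is not done.

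At stake are the by-visit GA tables and the GA MMRM. The comparison with historical progression planned in Protocol 11.3.2 is also exposed, but only if it uses those values.

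**Working it through.** The plan states no figure on this point, so there is none to reproduce.

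**Inputs from the documents.** Visits at Weeks 12, 24, 36, 48, 72 and 96 (Protocol 3.1); windows of ±7 days to Week 48 and ±30 days from Week 72; CSR data over 96 weeks (SAP 3.1); up to five subjects per dose-escalation cohort (Protocol 3.1).

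**Assumptions, not in the documents.** Linear growth, the share of subjects shifted, the spread of growth rates, image error, and any link between growth and leaving.

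**1. Largest relabelling distance.** Lag = gap in days − 1. Share of growth lost at the assigned visit = lag / (assigned week × 7), counting growth from dosing.

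| Gap | Largest lag | Growth lost |
|---|---|---|
| Week 12 to 24 | 83 d | 83/168 = 49.4% |
| Week 36 to 48 | 83 d | 83/336 = 24.7% |
| Week 48 to 72 | 167 d | 167/504 = 33.1% |
| Week 72 to 96 | 167 d | 167/672 = 24.9% |

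**2. Average moved value.** Fraction of true change carried = (exit week + L)/(assigned week + L), where L is the number of weeks from baseline FAF to dosing.

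- Exits spread evenly over the whole gap, L = 0: 60/72 = 83.3% and 84/96 = 87.5%.
- Exits outside every protocol window: 168 − 7 − 30 = 131 days between Weeks 48 and 72 (mean Week 58.36), and 168 − 60 = 108 days between Weeks 72 and 96 (mean Week 84).
 - L = 0: 58.36/72 = 81.1%; 84/96 = 87.5%.
 - L = 8: 66.36/80 = 83.0%; 92/104 = 88.5%.
 - L = 12: 70.36/84 = 83.8%; 96/108 = 88.9%.

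**3. Unadjusted group mean.** Fall = share shifted at that visit × (1 − fraction), L = 0, off-window exits.

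| Share shifted | Week 72 | Week 96 |
|---|---|---|
| 5% | 0.95% | 0.62% |
| 10% | 1.89% | 1.25% |
| 20% | 3.79% | 2.50% |

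One of five subjects is 20%. At the largest lag the fall is 0.20 × 33.1% = 6.6% at Week 72 and 0.20 × 24.9% = 5.0% at Week 96. A dose-by-route group stays at five only if the expansion cohort does not add to that dose.

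**4. MMRM by simulation.** Settings: 40,000 subjects in one group; FAF at Weeks 5, 12, 24, 36, 48, 72 and 96; lognormal slopes with CV 30 or 50%; image error SD 10 or 30% of 48-week growth; 5 to 20% leaving off-window between Weeks 48 and 96; unstructured covariance. Bias in the Week 96 mean:

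| Leaving | Relabelled | Image left out | Actual-time model |
|---|---|---|---|
| Unrelated to growth | −0.5 to −2.4% | within 0.1% | within 0.1% |
| Odds double per SD of faster growth | −0.7 to −3.5% | 0.0 to −1.4% | 0.0 to −0.4% |

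A second run differed in its settings: mean 1.7 mm²/year, 20% leaving evenly between Weeks 48 and 96, and a chance of leaving about 2.7 times higher per SD when related to growth. Relabelling gave 3.049 against a true 3.119 mm² (−2.2%) for unrelated exits, and 3.029 against 3.133 (−3.3%) when faster growers leave. Leaving the image out gave 3.120 and 3.115.

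**5. Where leaving the image out does worse.** All of these are cases in which faster progressors leave.

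- Unadjusted Week 96 mean, first simulation: low by 1.4 to 7.4% with the image left out, against 1.1 to 5.4% with relabelling.
- Unadjusted Week 96 mean, a third run (odds doubled per SD, 5 to 20% leaving): 2.4 to 6.6% against 1.8 to 5.1%.
- MMRM under the compound-symmetry fallback, same third run: 1.8 to 4.9% against 1.5 to 4.4%.

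**The case against.** **The bias may never arise.** If a programmer treats early termination as unscheduled, the closing paragraph of SAP 3.1.1 already removes these images from the by-visit outputs and the MMRM. This stands as a limit. However, the allocation sentence is the more specific rule, its trigger is itself a date off schedule, and it would have no work left in by-visit outputs if the exclusion overrode it. What is certain is that the SAP does not settle the matter.

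**The effect is small against sampling error.** With a growth CV of 30 to 50%, the standard error of a five-subject mean is 0.30/√5 = 13% to 0.50/√5 = 22% of mean growth. An average fall of 3.8% is under 0.3 standard errors. This also stands, although sampling error has no preferred direction and this error does.

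**The protocol wants withdrawn subjects' data shown.** Protocol 11.3 asks for their inclusion where possible and leaves the handling to the SAP, so the allocation rule can be read as carrying this out. That is a reason not to discard the images. The synopsis, however, lists early termination as an assessment category of its own, so a separate row meets the same aim without changing the date.

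**Leaving images out is not better everywhere.** Step 5 of the working confirms this, and the fix has to allow for it.

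**Stronger readings that the documents do not support.**

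- A reader might infer that the lag is unlimited. Visit spacing caps it at just under 24 weeks in the 96-week analyses; the 48-week gaps come later.
- A reader might infer that the trial's efficacy result is tilted towards GT005. The visible SAP gives the historical comparison no metric or time point, and a study-eye versus fellow-eye contrast is pulled towards zero.
- A reader might extend the direction to BCVA and LLVA, where it is uncertain.

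**Conclusion.** The point holds as a should-fix. SAP 3.1.1 contains two rules that can both apply to an off-schedule early-termination visit, and it does not rank them. If the allocation rule is followed, absolute study-eye GA growth is understated. The size is roughly 0.5 to 3.5% of the Week 96 unstructured-MMRM mean for 5 to 20% leaving off-window, and up to 6.6% of an unadjusted five-subject Week 72 mean with one subject shifted by the largest lag.

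These sizes rest on linear growth and on assumed exit shares, growth spread and image error. The documents give no rate of off-schedule termination, and the true share could be near zero. A subject who declines further follow-up at the Week 48 visit is not shifted, nor is an attendance that the site reports as a scheduled visit.

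The primary TEAE endpoint is unaffected. GA area is secondary, and SAP 3.1 rules out hypothesis testing. The historical comparison would lean towards GT005 only if it uses the relabelled values.

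**What to change.** Replace the allocation sentence in SAP 3.1.1 with wording such as:

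> An end-of-study assessment not made at a scheduled visit is assigned to a scheduled visit, in precedence over the unscheduled-visit rule, only if it falls within that visit's protocol window, the assessment is scheduled at that visit, and no value exists there. Otherwise it is left out of the MMRM and the scheduled-visit rows, shown in a separate early-termination row, listed, and used in any-time summaries.

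Footnote the by-visit GA tables with the number of images left out. Add a sensitivity model of square-root GA area on actual time since the baseline FAF, using every early-termination image at its true date. If outputs are already programmed, state in the CSR which rule was used and how many images were relabelled.

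The cost is one sentence, one derivation and one model. There will be a few fewer by-visit records and more reliance on the missing-at-random assumption in SAP 3.2. A subject whose only post-baseline FAF is an off-window early-termination image stays in the FAS but contributes only to the early-termination row, the listings, any-time summaries and the actual-time model. If faster progressors leave early, the unadjusted by-visit means, and the MMRM under a compound-symmetry fallback, can be slightly lower than with relabelling. They should therefore be read beside the actual-time model.
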